APPENDIX D. Grading of GVHD

Acute GVHD

For staging and grading the Glucksberg classification updated according to Przepiorka et al will be used⁴¹.

Stage	Skin	Liver	Intestinal Tract		
	Rash (% body surface)**	Total bilirubin (μmol/L)	Diarrhea	a (ml/day)	
1	< 25	34-50	500-1000 or persistent nausea without diarrhea *	280-555 ml/m ²	
2	25-50	50-102	1000-1500	556-833 ml/m ²	
3	> 50	102-255	> 1500	> 833 ml/m ²	
4	Generalized erythroderma with bullous formation	> 255	3. + severe abdominal pair	n / ileus	

^{*}persistent nausea with histologic evidence of GVHD in the stomach or duodenum

^{**} For a body surface area < 1.73 m² calculation per m²

Grade	
I	Skin: stage 1-2 and Liver: stage 0 and Gut: stage 0
П	Skin: stage 3 or Liver: stage 1 or Gut: stage 1
Ш	Liver: stage 2-3 or Gut: stage 2-4
IV	Skin or Liver: stage 4

Chronic GVHD

NIH consensus criteria for GVHD severity

A scoring system for chronic GVHD severity was created at a consensus conference supported by the National Institutes of Health (NIH) in 2005 and revised in 2014⁴².

The NIH GVHD scoring system includes information on the number of organs or sites involved and the severity within each affected organ (eg, skin, mouth, eyes, gastrointestinal tract, liver, lungs, joints/fascia, and genital tract)⁴². Organ specific severity is scored from 0 to 3 with higher scores reflecting more severe disease. Based upon this information, the overall severity is scored as mild, moderate, or severe:

- Mild Involves two or fewer organs/sites with no clinically significant functional impairment
- Moderate Involves three or more organs/sites with no clinically significant functional impairment or at least one organ/site with clinically significant functional impairment, but no major disability
- **Severe** Major disability caused by chronic GVHD

Grading of chronic GvHD as described by Jagasia et al.⁴² should be performed as described below.

	Score 0	Score 1	Score 2	Score 3			
Performance score: KPS ECOG LPS	Asymptomatic and fully active (ECOG 0; KPS or LPS 100%)	Symptomatic, fully ambulatory, restricted only in physically strenuous activity (ECOG 1, KPS or LPS 80 to 90%)	Symptomatic, ambulatory, capable of self-care, >50% of waking hours out of bed (ECOG 2, KPS or LPS 60 to 70%)	Symptomatic, limited self-care, >50% of waking hours in bed (ECOG 3 to 4, KPS or LPS <60%)			
Skin* Score % BSA GVHD features to be scored by BSA: Check all that apply: Maculopapular rash/erythema Lichen planus-like features Sclerotic features Papulosquamous lesions or ichthyosis Keratosis pilaris-like GVHD	□ No BSA involved	☐ 1 to 18% BSA	☐ 19 to 50% BSA	□ >50% BSA			
Skin features Score:	☐ No sclerotic features		Superficial sclerotic features "not hidebound" (able to pinch)	Check all that apply: Deep sclerotic features "Hidebound" (unable to pinch) Impaired mobility Ulceration			
Check all that apply: Hyperpigmentation Hypopigmentation Poikiloderma Severe or generalized pruritus Hair involvement Nail involvement	Hyperpigmentation Hypopigmentation Poikiloderma Severe or generalized pruritus Hair involvement						
Mouth Lichen planus-like features present:	☐ No symptoms	Mild symptoms with disease signs but not limiting oral intake significantly	Moderate symptoms with disease signs with partial limitation of oral intake	Severe symptoms with disease signs on examination with major limitation of oral intake			
Abnormality present but explained entirely by non-GVHD documented cause (specify):							
Abnormality present but expla			Score 3	Score 2			
	Score 0	Score 1	Score 2	Score 3			
Eyes Keratoconjunctivitis sicca (KCS) confirmed by ophthalmologist Yes No No Not examined			Score 2 Moderate dry eye symptoms partially affecting ADL (requiring lubricant eye drops >3 x per day or punctal plugs), WITHOUT new vision impairment due to KCS	Severe dry eye symptoms significantly affecting ADL (special eyeware to relieve pain) OR unable to			
Eyes Keratoconjunctivitis sicca (KCS) confirmed by ophthalmologist	Score 0 No symptoms	Score 1 Mild dry eye symptoms not affecting ADL (requirement of lubricant eye drops ≤3 x per day)	Moderate dry eye symptoms partially affecting ADL (requiring lubricant eye drops >3 x per day or punctal plugs), WITHOUT new vision impairment due to	Severe dry eye symptoms significantly affecting ADL (special eyeware to relieve pain) OR unable to work because of ocular symptoms OR loss of			
Eyes Keratoconjunctivitis sicca (KCS) confirmed by ophthalmologist Yes No Not examined GI tract Check all that apply: Esophageal web/proximal stricture or ring Dysphagia Anorexia Nausea Vomiting Diarrhea	Score 0 No symptoms	Score 1 Mild dry eye symptoms not affecting ADL (requirement of lubricant eye drops ≤3 x per day)	Moderate dry eye symptoms partially affecting ADL (requiring lubricant eye drops >3 x per day or punctal plugs), WITHOUT new vision impairment due to	Severe dry eye symptoms significantly affecting ADL (special eyeware to relieve pain) OR unable to work because of ocular symptoms OR loss of vision due to KCS Symptoms associated with significant weight loss ¶ > 15%, requires nutritional supplement for most calorie needs			
Eyes Keratoconjunctivitis sicca (KCS) confirmed by ophthalmologist Yes No Not examined GI tract Check all that apply: Esophageal web/proximal stricture or ring Dysphagia Anorexia Nausea Vomiting	Score 0 No symptoms ined entirely by non-GVHD d	Score 1 Mild dry eye symptoms not affecting ADL (requirement of lubricant eye drops <3 x per day) Symptoms without significant weight loss 1 (<5%)	Moderate dry eye symptoms partially affecting ADL (requiring lubricant eye drops >3 x per day or punctal plugs), WITHOUT new vision impairment due to KCS Symptoms associated with mild to moderate weight loss 5 to 15%) OR moderate diarrhea without significant interference	Severe dry eye symptoms significantly affecting ADL (special eyeware to relieve pain) OR unable to work because of ocular symptoms OR loss of vision due to KCS Symptoms associated with significant weight loss \$1 > 15%, requires nutritional supplement for most calorie needs OR esophageal dilation OR severe diarrhea with significant interference with daily			
Eyes Keratoconjunctivitis sicca (KCS) confirmed by ophthalmologist Yes No Not examined GI tract Check all that apply: Esophageal web/proximal stricture or ring Dysphagia Anorexia Nausea Vomiting Diarrhea Weight loss ≥5%¶ Failure to thrive	Score 0 No symptoms ined entirely by non-GVHD d	Score 1 Mild dry eye symptoms not affecting ADL (requirement of lubricant eye drops <3 x per day) Symptoms without significant weight loss 1 (<5%)	Moderate dry eye symptoms partially affecting ADL (requiring lubricant eye drops >3 x per day or punctal plugs), WITHOUT new vision impairment due to KCS Symptoms associated with mild to moderate weight loss 5 to 15%) OR moderate diarrhea without significant interference	Severe dry eye symptoms significantly affecting ADL (special eyeware to relieve pain) OR unable to work because of ocular symptoms OR loss of vision due to KCS Symptoms associated with significant weight loss \$1 > 15%, requires nutritional supplement for most calorie needs OR esophageal dilation OR severe diarrhea with significant interference with daily			
Eyes Keratoconjunctivitis sicca (KCS) confirmed by ophthalmologist Yes No Not examined GI tract Check all that apply: Esophageal web/proximal stricture or ring Dysphagia Anorexia Nausea Vomiting Diarrhea Weight loss ≥5%¶ Failure to thrive Abnormality present but explain	Score 0 No symptoms Indeed entirely by non-GVHD delined entirely enti	Score 1 Mild dry eye symptoms not affecting ADL (requirement of lubricant eye drops ≤3 x per day) Symptoms without significant weight loss 1 (<5%) Normal total bilirubin with ALT ≥3 to 5 x ULN or AP ≥3 x ULN	Moderate dry eye symptoms partially affecting ADL (requiring lubricant eye drops >3 x per day or punctal plugs), WITHOUT new vision impairment due to KCS Symptoms associated with mild to moderate weight loss 1 (5 to 15%) OR moderate diarrhea without significant interference with daily living	Severe dry eye symptoms significantly affecting ADL (special eyeware to relieve pain) OR unable to work because of ocular symptoms OR loss of vision due to KCS Symptoms associated with significant weight loss 1 > 15%, requires nutritional supplement for most calorie needs OR esophageal dilation OR severe diarrhea with significant interference with daily living			
Eyes Keratoconjunctivitis sicca (KCS) confirmed by ophthalmologist Yes No Not examined GI tract Check all that apply: Esophageal web/proximal stricture or ring Dysphagia Anorexia Nausea Vomiting Diarrhea Weight loss ≥5%¶ Failure to thrive Abnormality present but explain	Score 0 No symptoms Indeed entirely by non-GVHD delined entirely enti	Score 1 Mild dry eye symptoms not affecting ADL (requirement of lubricant eye drops ≤3 x per day) Symptoms without significant weight loss 1 (<5%) Normal total bilirubin with ALT ≥3 to 5 x ULN or AP ≥3 x ULN	Moderate dry eye symptoms partially affecting ADL (requiring lubricant eye drops >3 x per day or punctal plugs), WITHOUT new vision impairment due to KCS Symptoms associated with mild to moderate weight loss 1 (5 to 15%) OR moderate diarrhea without significant interference with daily living	Severe dry eye symptoms significantly affecting ADL (special eyeware to relieve pain) OR unable to work because of ocular symptoms OR loss of vision due to KCS Symptoms associated with significant weight loss 1 > 15%, requires nutritional supplement for most calorie needs OR esophageal dilation OR severe diarrhea with significant interference with daily living			
Eyes Keratoconjunctivitis sicca (KCS) confirmed by ophthalmologist Yes No Not examined GI tract Check all that apply: Esophageal web/proximal stricture or ring Dysphagia Anorexia Nausea Vomiting Diarrhea Weight loss ≥5%¶ Failure to thrive Abnormality present but explained Liver Lungs△	Score 0 No symptoms Indicate antirely by non-GVHD described entirely by non-GVHD described by Normal total bilirubin and ALT or AP <3 x ULN Indicate antirely by non-GVHD described by non-GVHD des	Score 1 Mild dry eye symptoms not affecting ADL (requirement of lubricant eye drops ≤3 x per day)	Moderate dry eye symptoms partially affecting ADL (requiring lubricant eye drops >3 x per day or punctal plugs), WITHOUT new vision impairment due to KCS Symptoms associated with mild to moderate weight loss¶ (5 to 15%) OR moderate diarrhea without significant interference with daily living Elevated total bilirubin but ≤3 mg/dL or ALT >5 ULN Moderate symptoms (shortness of breath after walking on flat	Severe dry eye symptoms significantly affecting ADL (special eyeware to relieve pain) OR unable to work because of ocular symptoms OR loss of vision due to KCS Symptoms associated with significant weight loss \$1.5%, requires nutritional supplement for most calorie needs OR esophageal dilation OR severe diarrhea with significant interference with daily living Elevated total bilirubin >3 mg/dL			

	Score 0	Score 1	Score 2	Score 3					
Joints and fascia P-ROM score (see below) Shoulder (1 to 7): Elbow (1 to 7): Wrist/finger (1 to 7): Ankle (1 to 4):	☐ No symptoms	Mild tightness of arms or legs, normal or mild decreased range of motion (ROM) AND not affecting ADL	Tightness of arms or legs OR joint contractures, erythema thought due to fasciitis, decrease ROM AND mild to moderate limitation of ADL	Contractures WITH significant decrease of ROM AND significant limitation of ADL (unable to tie shoes, button shirts, dress self, etc)					
☐ Abnormality present but exp	lained entirely by non-GVHD o	documented cause (specify):							
Genital tract Not examined Currently sexually active: Yes	☐ No signs	☐ Mild signs ♦ and females with or without discomfort on exam	Moderate signs of and may have symptoms with discomfort on exam	Severe signs with or without symptoms					
Check all signs that apply: Lichen planus-like featur Lichen sclerosis-like featur Vaginal scarring (female) Clitoral/labial agglutinatic Labial resorption (female) Abnormality present but exp	□ Lichen planus-like features □ Erosions □ Lichen sclerosis-like features □ Fissures □ Vaginal scarring (female) □ Ulcers □ Clitoral/labial agglutination (female) □ Phimosis (male) □ Labial resorption (female) □ Urethral meatus scarring/stenosis (male) □ Abnormality present but explained entirely by non-GVHD documented cause (specify): □ □ Abnormality present but NOT thought to represent GVHD (specify): □								
Other indicators, clinical fea									
severity (0 to 3) based on for Ascites (serositis) Pericardial effusion Pleural effusion(s) Nephrotic syndrome	☐ Myasthenia gravis_ ☐ Peripheral neuropa ☐ Polymyositis	thy	☐ Eosinophilia >	500/microL					
Overall GVHD severity (opinion of the evaluator)	☐ No GVHD	☐ Mild	☐ Moderate	Severe					
Photographic range of motion	on (P-ROM)								
Shoulder	rst) 2	3 4	5 6	7 (normal)					
Elbow 1 (wo	rst) 2	3 4	5 6	7 (normal)					
1 (wo	rst) 2	3 4	5	7 (normal)					
1 (wo	rst) 2	3 4 (normal)							

GVHD: graft-versus-host disease; KPS: Karnofsky Performance Status; ECOG: Eastern Cooperative Oncology Group; LPS: Lansky Performance Status; BSA: body surface area; ADL: activities of daily living; LFTs: liver function tests; AP: alkaline phosphatase; ALT: alanine aminotransferase; AST: aspartate aminotransferase; ULN: upper limit of normal.

* Skin scoring should use both percentage of BSA involved by disease signs and the cutaneous features scales. When a discrepancy exists between the percentage of total body surface (BSA) score and the skin feature score,

OR if superficial sclerotic features are present (score 2), but there is impaired mobility or ulceration (score 3), the higher level should be used for the final skin scoring.

 \P Weight loss within three months.

 Δ Lung scoring should be performed using both the symptoms and FEV1 scores whenever possible. FEV1 should be used in the final lung scoring where there is discrepancy between symptoms and FEV1 scores.

♦ To be completed by specialist or trained medical providers

APPENDIX E. Severity of viral infections

Viral infection severity grading

	Grade 1	Grade 2	Grade 3
HSV	Mucous HSV		Severe HSV (e.g. organ
			involvement, encephalitis,
			keratitis)
VZV	Dermatol zoster	VZV infection with 3 or more	Severe VZV (e.g.
		dermatomes	coagulopathy, encephalitis)
CMV*	Asymptomatic CMV viremia,	Clinically active CMV	CMV end-organ involvement
	with a > 66% decline of the	infection (e.g. symptoms,	(pneumonitis, enteritis,
	baseline value decline in	cytopenias) or asymptomatic	retinitis)
	viral load after 2 weeks of	CMV viremia, with less than	
	oral therapy with	66% decline of the baseline	
	valganciclovir, measured in	value decline in viral load	
	the week after cessation of	after 2 weeks of oral	
	therapy	therapy, , measured in the	
		week after cessation of	
		therapy OR asymptomatic	
		CMV viremia requiring	
		foscarvir	
EBV^	EBV reactivation not treated	EBV reactivation requiring	EBV PTLD
	with rituximab	rituximab	
AdV	Adenoviral conjunctivitis,	Adenoviral upper respiratory	Adenovirus with end-organ
	asymptomatic viruria,	infection, viremia OR	involvement (except
	asymptomatic stool	symptomatic viruria requiring	conjunctivitis and upper
	shedding and viremia not	treatment	respiratory tract)
	requiring treatment	il callient	respiratory tracty
HHV 6	Asymptomatic HHV-6 load	Clinically active HHV- 6	
ппу о	Asymptomatic firty-6 load		
		infection (e.g. symptoms,	
		cytopenias) OR HHV-6	
DI	BIX :	viremia requiring therapy	
BK	BK viremia or viruria with	BK viremia or viruria with	
	cystitis not requiring	clinical consequence	
	intervention	requiring (prolonged)	
		admission to the hospital	
		AND/OR urological	
		intervention	
Enterocolitis	Enterocolitis with virus	Enterocolitis with virus	
	present in the stool, not	present in the stool,	
	requiring intervention	requiring (prolonged)	
		admission to the hospital for	
		supportive care	
Respiratory	Respiratory tract viral	Respiratory tract viral	Respiratory tract viral

tract	infection with documented	infection with documented	infection requiring
infection	virus not requiring	virus requiring (prolonged)	mechanical ventilation
	intervention or admission to	admission to the hospital OR	
	the hospital	viral respiratory infection	
		complicated by a	
		documented bacterial	
		superinfection	
Viral	Documented viral infection	Documented viral infection	
infections	other as viral infections	other as viral infections	
not	defined above not requiring	defined above requiring	
specified	intervention or admission to	intervention or admission to	
above	the hospital	the hospital	

^{*}Definition CMV reactivation: viral load in blood > 250 IU/ml.

Severity of infections based on the grading according to the Bone Marrow Transplant Clinical Trials Network (BMT-CTN).

https://web.emmes.com/study/bmt2/public/Definition/Severity%20Grading_Recurrence%20Interval.pdf).

[^]Definition asymptomatic EBV reactivation: EBV detectable in blood not requiring treatment. EBV reactivation requiring treatment: EBV load > 1000 IU/ml OR detectable EBV load with clinical symptoms OR persistent elevated EBV load < 1000 IU/ml considered significant by the treating physician

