5. OBJECTIVE

5.1 Primary endpoint:

Cumulative incidence of severe viral infections (≥ grade 2 as in APPENDIX E) until day
 100

5.2 Secondary Endpoints:

- Engraftment
 - Time to neutrophil engraftment
 - Time to platelet engraftment
 - Donor engraftment (chimerism > 95%) at day 100
- Clinical outcome
 - o aGVHD until day 100
 - NRM until day 100
 - Number of graft failures until day 100
 - Event free survival (EFS: i.e. time from transplantation until progression/relapse, graftfailure or death from any cause, whichever comes first)
 - Overall survival (OS) calculated from transplantation. Patients still alive or lost to follow up are censored at the date they were last known to be alive Incidence of infections
 - Incidence and grade of chronic GvHD

- Long term NRM (1Y)
- Long term (secondary) graft failure (1Y)
- PK/PD
 - o ATG exposure
 - Fludarabine exposure
 - o Busulfan exposure
- Immunoreconstitution
 - Immune reconstitution including but not limited to total number of CD3⁺ T cells, CD4⁺ and CD8+ subtyping of T cells, CD3-CD16/56+ (NK cells), γδT-cells at 3, 6, 12 and 24 months after transplantation, assessment of NK and TCR repertoires at defined time points with personalized fludarabine conditioning.
 - Graft composition (CD34+ cells, αβ T cells, γδ T cells, NK cells, B cells)

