10. METHODS

10.1 Follow-up of primary end points

10.1.1 Severe viral infections (grade II-III according to appendix E)

Severity of infections based on the grading according to the Bone Marrow Transplant Clinical Trials Network (BMT-CTN). See appendix E

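### Appendix E grades some infections on both sides of the grade 2 line that defines the primary event: EBV above 1000 IU/ml not given rituximab, and adenoviral enterocolitis needing no intervention

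*Protocol*

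**What the plan says.** Protocol section 5.1 sets the primary endpoint as "Cumulative incidence of severe viral infections (≥ grade 2 as in APPENDIX E) until day" 100. The heading of section 10.1.1 repeats the cut: "Severe viral infections (grade II-III according to appendix E". Grade 1 is therefore a non-event, and grades 2 and 3 are events.

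Appendix E then grades by virus in some rows and by organ in others.

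- **EBV row.** Grade 1 is "EBV reactivation not treated" with rituximab. Grade 2 is "EBV reactivation requiring" rituximab. Grade 3 is PTLD.
- **EBV footnote.** Asymptomatic reactivation is EBV detectable in blood without need for treatment. Need for treatment is then defined: "EBV reactivation requiring treatment: EBV load > 1000 IU/ml OR detectable EBV load with clinical symptoms", with a third limb for a persistent load below 1000 IU/ml that the treating physician considers significant.
- **Adenovirus row, grade 3.** "Adenovirus with end-organ" involvement; only conjunctivitis and the upper respiratory tract are excepted.
- **Enterocolitis row, grade 1.** "Enterocolitis with virus" found in the stool and no intervention required. The row is not limited to any virus.

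Only the last row, for infections not specified above, excludes viruses that have their own row.

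**The concern.** An endpoint table should give each patient one answer. In two places this one gives two, and the two answers fall on opposite sides of the line between event and non-event.

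The setting gives the ambiguity room to matter. The trial is open label (section 6), and EBV and other viral infections are treated according to local protocols (section 8.8) at three centres, so the same EBV load may be treated at one site and observed at another. Whoever grades the infection may know the allocated arm and must still choose between two printed rules. What is at stake is the reproducibility of the primary outcome and its protection from a choice made with the arm known.

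**Working it through.** **1. The cut.** Event = Appendix E grade 2 or 3 by day 100 (sections 5.1 and 10.1.1).

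**2. EBV.** Take a patient with a load above 1000 IU/ml who is observed and not given rituximab.

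| Rule | Basis | Grade | Primary event? |
|---|---|---|---|
| Grade 1 cell | rituximab given or not | 1 | no |
| Grade 2 cell read with the footnote | need for treatment | 2 | yes |

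This reads the footnote's treatment as the row's rituximab. The footnote is attached to the EBV row, and rituximab is the only EBV treatment the row names, so that is the natural reading.

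**3. Adenovirus.** Take a patient with adenoviral enterocolitis, virus in the stool, needing no intervention.

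| Rule | Grade | Primary event? |
|---|---|---|
| Adenovirus row, end-organ involvement | 3 | yes |
| Enterocolitis row, no intervention required | 1 | no |

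The adenovirus row's own grade 1 covers asymptomatic stool shedding. It does not cover enterocolitis, so it does not resolve the conflict.

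**4. Tie-break.** Appendix E prints none between virus rows and organ rows. By contrast, the chronic GVHD notes in Appendix D say which score prevails when two skin scores, or lung symptoms and FEV1, disagree.

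**5. The design.** Inputs from section 12.1: failure proportions 40/90 = 0.4444 (arm A) and 15/90 = 0.1667 (arm B), n = 42 evaluable per arm, two-sided 0.05, Z test with pooled variance.

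Power = Φ[(|p1 − p2| − 1.96·√(2p̄(1 − p̄)/n)) / √((p1(1 − p1) + p2(1 − p2))/n)], with p̄ = 0.3056:

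- (0.2778 − 1.96 × 0.1005) / 0.0958 = 0.843, and Φ(0.843) = 0.800.

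The stated power is 81%, so the design reproduces to within about one point. No stated figure is disputed here.

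**6. Expected events.** 42 × (0.4444 + 0.1667) = 18.7 + 7.0 = 25.7, about 26. One patient is 1/42 = 2.4 percentage points of an arm; two are 4.8.

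**7. What one or two gradings can do.** Illustrative counts, using the design's pooled Z test (section 12.4.1 plans a Poisson model, which may give slightly different p-values):

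| Events A vs B (of 42 each) | z | two-sided p |
|---|---|---|
| 17 vs 8 | 0.2143/0.0998 = 2.15 | 0.032 |
| 17 vs 9 | 0.1905/0.1009 = 1.89 | 0.059 |
| 19 vs 7 (close to plan) | 0.2857/0.1009 = 2.83 | 0.005 |
| 19 vs 9 (two more in B) | 0.2381/0.1029 = 2.31 | 0.021 |

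Near the significance boundary, one grading decides the result. At the planned effect, two do not.

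**The case against.** **The EBV conflict is narrow.** Read whole, the footnote divides on need for treatment on both sides and can be taken to explain the row. A double grade arises only when a patient meets the footnote's definition and still does not receive rituximab. That is right, and it limits the scope. But the grade 1 cell still says not treated, and local treatment protocols make the case possible.

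**A tie-break could sit elsewhere.** The grading is based on an external BMT-CTN document, and eCRF instructions come separately (section 14.1). A missing rule alone would be no finding. Here, however, printed cells give opposite primary outcomes for the same patient.

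**The adenovirus case may be rare.** Scheduled PCR covers CMV and EBV only (section 10.4), and the historical series counted CMV, EBV or BK (section 4.1.2). That stands as a limit on weight. Also, a patient with another grade 2 infection is an event on either reading.

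The documents do not support three stronger inferences that a reader might draw:

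- **That adenoviral upper respiratory infection is a third conflict.** The grade 2 cell begins "Adenoviral upper respiratory" infection and ends with a need for treatment. If that condition applied to viruria alone, untreated viremia would be both grade 1 and grade 2. The parallel wording in grade 1 indicates that the condition covers the whole list, and then nothing conflicts.
- **That a given amount of power is lost.** Any such figure needs the share of patients in the overlap, which the Protocol does not give. The historical series was graded by CTC-AE v4.0, not Appendix E, so it cannot supply that share.
- **That the EBV conflict is purely about an objective number.** The footnote's third limb rests on physician judgement.

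**Conclusion.** Appendix E contradicts itself across the primary cut in two places: EBV load above 1000 IU/ml without rituximab (grade 1 and grade 2), and adenoviral enterocolitis needing no intervention (grade 3 and grade 1). The EBV case rests on equating the footnote's treatment with the row's rituximab; the adenovirus case needs no such assumption.

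The frequency is unknown, so the size can be given only as sensitivity. With about 26 expected events, each regraded patient moves an arm by 2.4 points, which is enough to change a borderline result but not one at the planned effect. This should be fixed. A reader might infer that the endpoint as a whole is unusable; nothing here shows that.

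**What to change.** For endpoint classification only, with no change to how any patient is treated:

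1. Reconcile the EBV row with its footnote so that grades 1 and 2 use one and the same criterion. The sponsor chooses whether that is treatment given or need as defined, and states whether the physician-judgement limb is kept or removed. Dropping that limb silently could turn a patient given rituximab for a persistent lower load from an event into a non-event.
2. State one precedence rule for overlapping rows. For example, a virus-specific row governs over the enterocolitis and respiratory rows, and the highest grade is taken only within the governing row or across separate infections. An unrestricted highest-grade rule would conflict with row precedence: an HHV-6 respiratory infection needing ventilation is at most grade 2 in its own row and grade 3 in the respiratory row.
3. Have the infection CRF capture what these rules need. Section 11.2.2 names that CRF, but the Protocol does not say whether it records viral loads or the reason for treatment.

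The cost is a few sentences in Appendix E plus matching CRF instructions, and possibly added CRF fields. Because sites may grade infections as they occur, the wording should be settled before infections are graded.
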